## 7. Statistical Plan

### 7.1. Power

A power analysis is provided only for the primary aims because the exploratory aim is hypothesis generating. Most of our power calculations were approximated as 2-sided t- or z-tests, with  $\alpha = 0.05$ , using PASS Software (Power and Sample Size, NCSS Software, Kaysville, UT). Equivalence testing was approximated as two one-sided tests, with  $\alpha = 0.025$  each.

#### 7.1.1. Aim 1:

The primary efficacy analysis (**H1**) is a comparison in week 10 (of treatment) and week 24 post-TQD of CO-confirmed 7-day point prevalence quit rates for the placebo and bupropion groups. For the week-10 comparison, we expect that the quit rates in the placebo and bupropion arms would approximate those reported in bupropion trials in the general population of smokers (i.e., placebo = 21.2%; bupropion = 35.9%, OR = 2.1; ref. 44). A sample of 360 provides 88% power to detect a significant between-group effect. The OR for bupropion treatment is similar at 24 weeks, based on Jorenby et al. (168) and our own data, and results from 10 and 24 weeks are highly correlated ( $\rho > 0.7$ ). Thus, we have 80% power to detect a significant difference between treatment arms.

Safety analyses (**H2**) will examine maternal safety across the 10-week treatment and 24-week follow-up periods and fetal and birth outcomes. Key maternal and fetal outcomes to be compared across treatment groups include rates of moderate-to-severe side AEs of bupropion (from the AE checklist). Key birth outcomes will include Apgar scores, birth weight, duration of pregnancy, rate of obstetrical complications, and need for NICU admission. These analyses will involve a test of equivalence because we cannot use standard statistical tests to conclude that a non-significant comparison shows that the drug is safe (i.e., "the absence of evidence is not evidence of its absence"). In our past study with bupropion, 45% of bupropion-treated participants reported no moderate-to-severe AEs, vs. 47% of participants on placebo, a 2% difference. With the present sample size, we will have 82% power to detect similar equivalence between treatment arms on the frequency of moderate-to-severe AEs over the course of the trial, given that AEs are not significantly different between treatment arms, using an equivalence window of 0.30 to 0.60. Likewise, Oncken et al. (47) reported 38% AEs for the placebo group

CONFIDENTIAL

and 25% in the nicotine group. An equivalence test with placebo and bupropion groups both at 30% and an equivalence window for bupropion of +/-15% provides 81% power.

For **H3**, we have very high power. Oncken et al. (47) found a difference in birth weight between groups of 337 g, which yields an effect size  $> d=0.5$ . The power to detect a difference of that magnitude will exceed 99%, and we have 80% power to detect a difference as small as 180 grams. We also have >89% power to detect differences in secondary analyses of the frequency of low birth weight and preterm delivery.

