## **4. Participant Selection and Withdrawal**

### **4.1. Inclusion Criteria**

1. Currently smoking on average 3 or more cigarettes per day for the preceding 7 days with a breath CO of at least 5 ppm and wants to quit smoking
2. Pregnant at 13-26 weeks gestation (to maximize safety and the likelihood of receiving 10 weeks of treatment)
3.  $\geq 18$  years of age
4. Able to speak and read English at a 6th grade level or higher, using the Slosson Oral Reading Test (SORT)
5. Committed to remaining in the geographic area for at least 3 months postpartum
6. Able to sign written informed consent and commit to completing the procedures involved in the study.
7. Methadone or buprenorphine-maintained women must be in methadone or buprenorphine treatment for a minimum of 2 weeks prior to entering the study. Their 2 most recent urine drug screens, consecutive and administered at least one week apart, must both be positive for methadone or buprenorphine and negative for drugs of abuse other than cannabis. Participants who screen positive for other drugs at either time point will not be enrolled in the study until they meet this criterion.

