### **4.3. Participant Recruitment and Screening**

All sites will have a senior clinician to oversee the integration of the trial into clinical practice. Approval from the City of Philadelphia Institutional Review Board and the Health Commissioner's Office will be obtained given the involvement of Philadelphia Department of Public Health data, staff, and clients at the Jefferson MATER site, where methadone-maintained pregnant smokers will be enrolled. Buprenorphine-treated subjects will be recruited from the "Mothers MATTER" program at the Dickens clinic and from the Jefferson MATER site. As in our previous successful clinical trials (e.g., 14, 47, 52), we will use experienced and trained research staff to identify and screen potentially eligible participants in the clinics. Recruitment sites will also be provided with IRB-approved materials designed to raise awareness of the study, including posters and brochures to be displayed prominently in all clinic areas. We will also encourage referrals from clinicians in the surrounding areas at each site, and will recruit through newspapers, maternity magazines and social media. Interested and potentially eligible participants will be scheduled for an intake session (week -1) to determine eligibility. For details on Screening, see 6.2 Informed Consent and Screening Visit below.

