### 5.3. Method for Assigning Participants to Treatment Groups

Participants will be randomly assigned to one of two treatment conditions: Bupropion 300 mg/day (n = 180) or placebo (n = 180). We will use small-block randomization by site (Penn or MATER) provided by [name], the study biostatistician. A PHQ-9 score of 10 or greater will be used to identify major depression and stratify the randomization on it. Study site (Penn or MATER) will be the second of the two stratification variables. Study staff and the Investigational Drug Service (IDS) staff will be responsible for medication randomization. The process for randomization is: 1) The research coordinator will complete a “randomization form,” which includes the variables to be entered into the randomization program and fax or email the form without protected health information to the UPenn site; 2) A designated study staff member

Table 1: Medication Dispensing Schedule

	Medication Dispensed For	Morning Dose	Evening Dose	Total Daily Dose
Visit A: Screening	N/A	No medication	No medication	
Visit B: Baseline	Wk 1	150 mg	No medication (for first 3 days); then 150 mg	150 mg
Visit C: Wk 1	Wk 2 through Wk 5	150 mg	150 mg	300 mg
Visit D: Wk 3	N/A	N/A	N/A	N/A
Visit E: Wk 5	Wk 6 through Wk 10	150 mg	150 mg	300 mg
Visit F: Wk 7		150 mg	150 mg	300 mg
Visit G: Wk 10	Endpoint	No medication	No medication	N/A

CONFIDENTIAL

This material is the property of the University of Pennsylvania. Do not disclose or use except as authorized in writing by the study sponsor

Visit H: Wk 24 Post-TQD	N/A	No medication	No medication	N/A
Visit I: 2 wk postpartum	N/A	No medication	No medication	N/A
Visit J: 6 wk postpartum	N/A	No medication	No medication	N/A

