We will post and distribute recruitment material in community settings with public posting areas or other means of providing community access to materials (such as town halls, public libraries, YMCAs, health fairs). We will obtain permission at select locations before distributing or posting the approved recruitment materials (ensuring compliance with other institutions guidelines, including seeking IRB approval as needed to conduct recruitment activities). We will also encourage referrals from clinicians in the surrounding areas at each site including Penn Family Medicine. At the Jefferson site, we will recruit patients from MATER (Maternal Addiction, Treatment, Education and Research, which provides methadone maintenance treatment for pregnant women), part of the Pediatrics Department. MATER is located at [name], which is where recruitment will take place and treatment will be delivered. We will also recruit patients from Jefferson University Department of Obstetrics and Gynecology Associates (JOGA). We will conduct a brief in-person pre-screening questionnaire and a screening interview over the phone or in-person at the participant's obstetrics clinic to assess study eligibility criteria. At Jefferson, medical records will be reviewed for gestational age and smoking status to identify prospective participants. Prospective participants who appear to meet eligibility criteria for the study will be scheduled for an in-person Informed Consent and Screening visit. See Table 2 below for the schedule of assessments. Buprenorphine-treated women will be recruited through the Penn and Jefferson MATER sites as described above.

CONFIDENTIAL

This material is the property of the University of Pennsylvania. Do not disclose or use except as authorized in writing by the study sponsor

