### **Adverse Event – Neonate**

An **adverse event** (AE) is any symptom, sign, illness or experience that develops or worsens in severity during gestation or at birth. Intercurrent illnesses or injuries should be regarded as adverse events. Abnormal results of diagnostic procedures are considered to be adverse events if the abnormality:

- results in study withdrawal
- is associated with a serious adverse event
- is associated with clinical signs or symptoms
- leads to additional treatment or to further diagnostic tests
- is considered by the investigator to be of clinical significance
- results in prolonged hospitalization in the NICU due to neonatal abstinence syndrome (expected for babies exposed to methadone or buprenorphine) or premature birth (expected for babies whose mothers' smoke)
- conditions associated with premature birth, such as patent ductus arteriosus

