### **Serious Adverse Event – Neonate**

Adverse events are classified as serious or non-serious. A **serious adverse event** is any AE develops or worsens in severity during gestation or at birth that is:

- fatal
- life-threatening
- requires or prolongs hospital stay in the NICU (except for neonatal abstinence syndrome)
- results in persistent or significant disability or incapacity
- results in a congenital anomaly or birth defect
- results in any unexpected condition not explained by gestational history

Important medical events are those that may not be immediately life threatening, but are clearly of major clinical significance. They may jeopardize the participant wellbeing, and may require intervention to prevent one of the other serious outcomes noted above. For example, drug overdose or abuse, a seizure that did not result in inpatient hospitalization, or intensive treatment of bronchospasm in an emergency department would typically be considered serious.

CONFIDENTIAL

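### NICU admission is compared between arms without separating neonatal abstinence syndrome, although opioid-maintained women are eligible and the protocol expects such stays in their infants

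*Combined protocol and SAP*

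**What the plan says.** Eligibility (4.1, criterion 7): "Methadone or buprenorphine-maintained women must be in methadone or buprenorphine treatment for a minimum of 2 weeks prior to entering the study".

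Recruitment: section 4.3 places methadone recruitment "at the Jefferson MATER site, where methadone-maintained pregnant smokers will be enrolled". It recruits buprenorphine-treated women from a "program at the Dickens clinic and from the Jefferson MATER site", and section 6.1 repeats that "Buprenorphine-treated women will be recruited through the Penn and Jefferson MATER sites as described above".

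Randomisation (5.3): one stratification variable is a PHQ-9 score of 10 or more. For the other, "Study site (Penn or MATER) will be the second of the two stratification variables".

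Outcome: section 3.2 lists NICU admissions among the birth outcomes, and 7.1.1 makes them a key outcome for H2: "Key birth outcomes will include Apgar scores, birth weight, duration of pregnancy, rate of obstetrical complications, and need for NICU admission". Neither refers to the cause of admission. Section 7.1.1 says these safety analyses involve a test of equivalence, and 7.1 sets two one-sided tests at 0.025 each. Section 7.2.2 describes the H2 test only for adverse events, on the odds-ratio scale; it gives no NICU margin.

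Safety definitions (8.1): a neonatal adverse event includes one that "results in prolonged hospitalization in the NICU due to neonatal abstinence syndrome (expected for babies exposed to methadone or buprenorphine"). A neonatal serious adverse event includes one that "requires or prolongs hospital stay in the NICU (except for neonatal abstinence syndrome").

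Covariates: 7.2 and 7.2.2 provide for adjustment for variables found to be related to treatment arm or to differ between arms. The examples in 7.2.2 do not include opioid maintenance.

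**The concern.** The protocol recognises that some NICU stays in this population follow from maternal opioid treatment, and sets them aside when classifying serious events. That distinction is not carried into the between-arm comparison of NICU admission.

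If NAS admissions occur at the same rate in both arms, they add the same background to each. The difference in other admissions shrinks and the variance rises. In a superiority analysis this costs power. In an equivalence analysis, dilution is not conservative, because it moves the estimate towards the conclusion that the arms are alike. At stake is whether a rise in other NICU admissions on bupropion would be recognised in a trial meant to inform fetal and neonatal safety. The added variance also makes it harder to show equivalence when the arms truly do not differ.

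**Working it through.** **No figure to reproduce.** The documents give no NICU rate, NICU margin, NICU power or expected share of opioid-maintained women. The only design input they supply is 180 per arm (5.3). All rates below are assumptions.

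**Model.** Let *a* be the rate of NICU admission for other reasons, *s* the share of women who are opioid-maintained, and *b* the chance of NAS admission in their infants. Take NAS admission as independent of arm and of other causes. With m = s × b, the all-cause rate is

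q = 1 − (1 − a)(1 − m),

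so the risk difference shrinks by the factor (1 − m).

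**Superiority power** (two-sided 0.05, n = 180 per arm, q̄ the mean of the two rates):

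Φ{[(q1 − q0) − 1.96·√(2q̄(1 − q̄)/n)] / √(q0(1 − q0)/n + q1(1 − q1)/n)}

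- Other admissions only, 12% vs 24%: (0.120 − 1.96 × 0.0405)/0.0400 = 1.016, power 85%.
- One third opioid-maintained and b = 60% (m = 20%): q = 29.6% vs 39.2%; (0.096 − 1.96 × 0.0501)/0.0498 = −0.043, power 48%.

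**Chance of declaring equivalence** (two one-sided tests at 0.025):

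Φ[(Δ − d)/se − 1.96] + Φ[(Δ + d)/se − 1.96] − 1

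Here *d* is the true difference, on the risk-difference scale with Δ = 15 points or on the log-odds scale with Δ = log 1.91. The 15 points are borrowed from the adverse-event example in 7.1.1. The limit 1.91 is the odds ratio of 45% to 30%: (0.45/0.55)/(0.30/0.70).

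| s | b | m | All-cause rates | OR | Superiority power | Declared equivalent, ±15 points | Declared equivalent, OR 1.91 |
|---|---|---|---|---|---|---|---|
| 0 | – | 0 | 12.0% vs 24.0% | 2.32 | 85% | 11% | 0.4% |
| 5% | 40% | 2% | 13.8% vs 25.5% | 2.15 | 80% | 12% | 0.8% |
| 10% | 60% | 6% | 17.3% vs 28.6% | 1.91 | 72% | 13% | 2.3% |
| 20% | 40% | 8% | 19.0% vs 30.1% | 1.83 | 68% | 14% | 3.6% |
| 1/3 | 60% | 20% | 29.6% vs 39.2% | 1.53 | 48% | 19% | 16% |
| 50% | 60% | 30% | 38.4% vs 46.8% | 1.41 | 36% | 24% | 29% |

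**Other scenarios on the ±15-point scale.**

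- A harm exactly at the margin (10% vs 25%) is wrongly called equivalent 2.5% of the time without NAS admissions, and 3.7% to 16.7% of the time for m = 5% to 35%.
- For 10% vs 20%, the chance moves little: from 27% to 27-35% over the same range.
- If the arms truly do not differ (10% each), power to show equivalence falls from 99.5% to 87% at m = 12.5% and 65% at m = 35%.

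**Value of the covariate.** In the one-third scenario, simulated logistic regressions of all-cause admission put superiority power at about 48% unadjusted and about 58-60% with opioid maintenance as a covariate.

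**The case against.** **The size is assumed.** This stands. MATER is only one of several recruitment locations; the Study Summary also lists Penn clinics, another Jefferson practice and a Delaware hospital system. The opioid-maintained share could be small, and at 5-10% the loss is modest.

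**Superiority power is not the planned analysis.** This also stands. A reader might infer that H2 power falls from 85% to about 48%. The documents do not support that: the plan specifies two one-sided tests, gives no NICU margin, and under those tests the effect is small on one scale and marked on the other.

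**Randomisation and adjustment deal with imbalance.** Largely right. A reader might infer that opioid exposure is left unbalanced, or that it confounds the comparison. Randomisation balances it on average. Methadone recruitment is described only at MATER, so the site stratum largely balances that group. Sections 7.2 and 7.2.2 allow adjustment for observed imbalance, including in the birth-weight regression. What remains is dilution of the NICU outcome, plus the weaker point that adjustment is left to be triggered by the data.

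**Serious adverse event data would show the harm.** Partly. A NICU stay for another reason is a neonatal serious adverse event, and the monitoring board receives a summary of all adverse events. But 8.1 runs adverse event reporting to the last assessment, whereas the serious adverse event reporting period in section 10 ends 28 days after study drug stops. A woman starting at 20 weeks would stop at 20 + 10 = 30 weeks and leave that window at 34 weeks, before a term birth. Coverage is therefore uncertain.

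**Bupropion might affect NAS.** A reader might infer that NAS admissions cannot depend on the drug and should be removed from the endpoint. Nothing in the documents shows this. If the drug did raise NAS admissions, removing them would hide a harm. All-cause admission needs no attribution of cause and is a defensible safety outcome, so it should stay.

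**Conclusion.** The concern holds as a gap in the definition and analysis of one key safety outcome. The protocol separates NAS stays when classifying neonatal serious events but not when comparing NICU admission between arms, and opioid maintenance is not a named covariate for any birth outcome. If NAS admission does not depend on arm, the all-cause comparison is less sensitive to a difference in other admissions, and in an equivalence comparison that loss favours a finding of no difference.

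The size rests wholly on the assumed rates: minor if few opioid-maintained women enrol, substantial if they form a fifth or more of the sample. The effect on the planned tests cannot be fixed until a NICU margin and scale are stated. The finding is one of lost sensitivity; it does not show a biased randomised comparison.

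**What to change.** 1. Keep all-cause NICU admission in 3.2 and 7.1.1.
2. Pre-specify beside it a between-arm comparison of NICU admission for reasons other than NAS alone, using the exclusion already in the neonatal serious adverse event definition. Have cases with both NAS and another reason classified blinded to arm.
3. Report NAS admissions separately by arm, so that any drug effect on NAS stays visible.
4. Name opioid-maintenance status, already established under criterion 7, as a covariate in the NICU, birth-weight and preterm models, instead of relying only on adjustment for observed imbalance.
5. State the NICU equivalence margin and its scale, or say that the NICU comparison is descriptive.

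The cost is wording, one extra covariate, one extra comparison and some judgement in mixed cases. Section 3.2 lists only NICU admissions as taken from the delivery records, so the data form should also record the reason; serious-event classification already needs it. Eligibility, treatment and visits do not change.

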**H2:** We will compare treatment arms for equivalence of the frequency of moderate-to-severe AEs (individual and total). The hypothesis test for equivalence is a test of whether the OR is out of the prescribed range for the difference between the treatment arms. Using logistic regression, we will conduct two one-sided tests against predefined upper and lower equivalence boundaries on percent reporting only mild AEs. The test-statistic will be the z-score corresponding to the log of the OR. This provides a more valid test of the potential safety of bupropion for pregnant smokers than a simple comparison of mean responses on a measure of AEs.

**H3:** Mean birth weight will be compared for treatment groups using a two-sample t-test, in the context of multiple linear regression. The regression format allows us to add covariates to adjust for imbalances in participant characteristics between treatment arms. Treatment will be entered as a binary indicator. In a secondary analysis, we will also compare the percentage of participants in each group that delivers an infant of LBW (1500-2500 g) or preterm delivery. These secondary hypotheses will be tested using the z-score corresponding to the OR that will be estimated using logistic regression.

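### The stated 82% and 81% power for the H2 safety equivalence test is not delivered: two one-sided tests at 0.025 with 180 per arm give about 63–68% and 75–77%

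*Combined protocol and SAP*

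**What the plan says.** Section 7.1 describes the method for the safety power: "Equivalence testing was approximated as two one-sided tests", with alpha of 0.025 for each test. Section 7.1.1 then gives two examples.

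- Example 1 takes its rates from an earlier bupropion study: "45% of bupropion-treated participants reported no moderate-to-severe AEs, vs. 47% of participants on placebo, a 2% difference". The claim for the present sample size is that "we will have 82% power to detect similar equivalence between treatment arms on the frequency of moderate-to-severe AEs", "using an equivalence window of 0.30 to 0.60".
- Example 2 sets both arms at a 30% adverse event rate and states that "an equivalence window for bupropion of +/-15% provides 81% power".

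Section 5.3 allocates 180 women to each arm. Section 7.2.2 carries the same procedure into the analysis: "we will conduct two one-sided tests against predefined upper and lower equivalence boundaries". The statistic there is the z-score of the log odds ratio from a logistic regression.

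**The concern.** An equivalence claim needs both boundaries to be rejected, so its power is the probability of the joint event. That is always lower than the power of the weaker single test unless the other test is almost certain to reject. Here the window is only about 15 percentage points on either side of the assumed rate. Neither test in example 1 is near certainty, so the joint requirement costs a lot of power. The stated 82% and 81% look like single-test figures.

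H2 is a named hypothesis under Specific Aim 1, and section 3.2 lists moderate or severe side effects among the primary endpoints. Section 7.1.1 chooses an equivalence test because a non-significant difference would not establish safety. The trial's formal maternal safety conclusion therefore rests on this test. A reader relying on the stated power would underestimate how often the test fails when the drug is as well tolerated as assumed, and might read such a failure as a safety signal.

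**Working it through.** **Inputs.** n = 180 per arm (section 5.3); alpha = 0.025 per one-sided test, critical value 1.96 (section 7.1); rates and windows from section 7.1.1; test scale from section 7.2.2. The window of 0.30 to 0.60 is read as the bupropion proportion. Against a placebo rate of 0.47 it gives difference margins of −0.17 and +0.13.

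**Formula.** With z_U and z_L the distances from the true effect to the upper and lower bounds in standard errors:

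P(both reject) = Φ(z_U − 1.96) + Φ(z_L − 1.96) − 1

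**Example 1 (45% vs 47%), difference scale**
- SE = √(0.45×0.55/180 + 0.47×0.53/180) = 0.0525
- True difference −0.02, so each bound is 0.15 away: z_U = z_L = 0.15/0.0525 = 2.86
- Each single test: Φ(2.86 − 1.96) = 0.815
- Both: 2 × 0.815 − 1 = **0.630**

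**Example 1, log-odds-ratio scale**
- SE = √(1/(180×0.45×0.55) + 1/(180×0.47×0.53)) = 0.2115
- True log OR = −0.0805; bounds implied by 0.30 and 0.60 against 0.47 are −0.727 and 0.526 (OR 0.48 and 1.69)
- z_U = (0.526 + 0.0805)/0.2115 = 2.87, single test 0.817
- z_L = (0.727 − 0.0805)/0.2115 = 3.06, single test 0.864
- Both: 0.817 + 0.864 − 1 = **0.681**

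**Example 2 (30% vs 30%, ±15 points), difference scale**
- SE = √(2×0.30×0.70/180) = 0.0483; z = 0.15/0.0483 = 3.105
- Each single test 0.874; both: 2 × 0.874 − 1 = **0.748**

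**Example 2, log-odds-ratio scale**
- SE = √(2/(180×0.30×0.70)) = 0.230; bounds −0.887 and 0.647 (OR 0.41 and 1.91)
- z_U = 2.81, single test 0.803; z_L = 3.86, single test 0.971
- Both: 0.803 + 0.971 − 1 = **0.774**

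**Reproducing the plan's figures**

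| Procedure, 180 per arm | Example 1 (stated 82%) | Example 2 (stated 81%) |
|---|---|---|
| Both tests, 0.025 each, difference | 63.0% | 74.8% |
| Both tests, 0.025 each, log OR | 68.1% | 77.4% |
| Upper-bound test only, 0.025, log OR | 81.7% | 80.3% |
| Both tests, 0.05 each, difference | 77.4% | 85.6% |
| Both tests, 0.05 each, log OR | 81.0% | 86.5% |

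Of these, only the single upper-bound test comes near both stated figures.

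**Exact check.** Enumerating all binomial outcomes gives, on the difference scale, 63.4% and 74.7%. On the log-odds-ratio scale it gives 67.0% and 76.8% without a cell correction, and 68.7% and 77.3% with 0.5 added to each cell. The normal approximation is not the source of the gap.

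**Sample size for the stated power.** With both tests at 0.025, 82% in example 1 needs about 241 per arm (difference) or 225 (log OR). For 81% in example 2 it is about 200 or 194.

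**Sensitivity.** Centring ±15 points on the placebo rate, with 45% vs 47%, lowers example 1 to 59.6%. No dropout is included above. If, as an assumption, 20% of women had no usable adverse event data (144 per arm), the joint power would be about 45–51% and 59–64%.

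**The case against.** **Example 2 is a small gap.** On the planned log-odds-ratio scale it is 77.4% against 81%, under 4 points. Section 7.1.1 also qualifies its power as holding when adverse events do not differ significantly between arms. Conditional on a non-significant difference, example 2 gives about 79–81%. But that qualification stands in the sentence on example 1, where conditioning gives only about 67–72%. The analysis in section 7.2.2 is also unconditional. The clause does not rescue the 82%, and it reaches the 81% only if carried over to another sentence.

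**The planned scale is the log odds ratio.** This is fair. On that scale the example 1 shortfall is about 14 points rather than 19, and the failure rate about 32%.

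**The cause is inferred.** The software output is not in the documents. A misprinted alpha is another possible explanation: 0.05 per side gives 81.0% for example 1 on the log-odds-ratio scale. It contradicts section 7.1 and gives about 86% for example 2, so it does not explain both figures. How the figures arose stays an inference; that the stated procedure does not deliver them is arithmetic.

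**Error control is unaffected.** Also true. Low power does not make a false claim of equivalence more likely, and the sample of 360 also serves H1 and H3. The defect is a wrong planning figure for a named hypothesis, not an invalid test.

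**Conclusion.** The concern holds. As specified, the H2 test has about 63–68% power in example 1, against the stated 82%, and 75–77% in example 2, against the stated 81%. Under the plan's own assumptions, the chance of failing to show equivalence is 32–37% rather than 18% in example 1, and 23–25% rather than 19% in example 2. Example 1 is the clear and material error; example 2 is wrong in the same direction by 4 to 6 points. The result assumes 180 evaluable women per arm, 0.025 for each test, and the 0.30 to 0.60 window applied to the bupropion proportion.

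**What to change.** In section 7.1.1, restate the H2 power as about 63–68% for example 1 and 75–77% for example 2, and say that it is the probability that both tests reject. State the scale, and give the boundaries as odds ratios so that they match the test in section 7.2.2. The windows in section 7.1.1 imply roughly 0.48 to 1.69 for example 1 and 0.41 to 1.91 for example 2. Say whether the qualification about non-significant differences is meant to condition the power. Add the figure for the expected amount of missing adverse event data. This costs one paragraph and a less favourable stated power. Keeping the stated power instead would need the larger samples given above.

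A separate design choice, not required to correct the error, is a one-sided non-inferiority test at 0.025 against the harm boundary. On the same inputs it has 81–86% power in example 1 and 80–87% in example 2, for one more changed sentence in section 7.2.2. It gives up any formal claim in the other direction, and so replaces the equivalence claim with a weaker one.
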